Secondary endpoints	Proportion of participants achieving urate levels of $\leq 0.3\text{mmol/L}$ at 52wks (and for extension 104wks and 156wks) Medication compliance assessed by patient self-report and serum oxypurinol Number of days of self-reported gout flare Size in mm of the largest tophus (index tophus) and number of clinically evident tophi Self-reported quality of life during/following gout flare evaluated using the EQ-5D-5L questionnaire Number of days lost at work and number of scheduled and unscheduled medical appointments or hospital admissions due to gout Proportion of patients achieving a dose reduction of urate lowering therapy in the extension phase Proportion of patients achieving sustained dietary modifications and relative reduction of urate lowering therapy in the extension phase.
Device name	BeneCheck plus
Manufacturer name	General Life Biotechnology Co Ltd, Taiwan
Principle intended use	Self-management of gout by patients in the community managed by the general practitioner

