1 INTRODUCTION

1.1 BACKGROUND AND RATIONAL

Gout is the most common cause of inflammatory arthritis with prevalence in the UK estimated at 2.5%, and an incidence that is rising globally alongside epidemics of obesity and cardiovascular disease. For patients it is characterised by sudden attacks of pain of great intensity, and is a cause of reduced quality of life, work absence and disability. For health services gout is an increasing cause of emergency attendance, hospital admission, and prolonged hospital stays. Recent guidelines have emphasised the importance of maintaining urate below target levels in order to achieve long term prevention of gout attacks (Khanna J, 2012). Within clinical trials or with sufficient support it is clear that the vast majority of patients are able to achieve target serum urate levels, though in routine clinical practice patients rarely meet current recommendations. High levels of serum urate can result in the formation of urate crystal deposits under the skin (called tophi) which are a marker of severe disease. These will resolve if serum urate levels are held low for a sustained period of time. Tight control of gout with a target of urate at or below 0.3mmol/l should achieve disease remission (clearance of all crystals from the body), but once this has been achieved recent guidelines suggest that keeping urate levels at or below 0.36mmol/l should prevent recurrence of disease. There is no consensus on how long tight control of urate is required, nor is there published experience of long term disease related outcomes in gout patients that have achieved target urate levels.

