2.2 ENDPOINTS

2.2.1 Primary Endpoint

- Proportion of participants achieving urate level $\leq 0.30\text{mmol/L}$ at 24 weeks.

2.2.2 Secondary Endpoints (assessed at week 24 and 52, and for extension study also at week 104 and 156)

- Proportion of participants achieving urate level $\leq 0.3\text{mmol/l}$ and $\leq 0.36\text{mmol/l}$
- Prospectively gathered number of days of self-reported gout flare over course of study
- Size in mm of the largest tophus at baseline (index tophus)
- The number of clinically evident tophi
- Prospectively gathered self-reported quality of life during/following gout flare evaluated using the EQ-5D-5L questionnaire over course of study
- Prospectively gathered data on days lost at work due to gout flare over course of study
- Prospectively gathered number of scheduled and unscheduled medical appointments/ hospital admissions due to gout over course of study
- Self report of number of doses of medication omitted in preceding 2 weeks will be collected at all study visits
- Plasma oxypurinol levels will be measured at study visits where possible
- Proportion of patients achieving a dose reduction of urate lowering therapy in the extension phase whilst maintaining target urate levels.
- Proportion of patients achieving sustained dietary modifications with reduction of urate levels, and/or further reduction of urate lowering therapy dose in the extension phase.

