3.2 Extension phase

Urate-lowering therapy requires a long term commitment from the patient and health care provider. We know that levels of medication adherence in gout are unusually low (Dehlin M, 2017 and Briesacher BA, 2008). A recent randomised controlled trial comparing specially trained nurses leading care versus usual care in the UK, showed that with dedicated surveillance and monitoring, the use of urate lowering therapy is significantly higher at 1 and 2 years in the nurse-led compared to the usual care group (Doherty M, 2018). The GoutSMART approach may provide an alternative means for patients to monitor their disease and increase awareness of the role and importance of long-term urate lowering therapy for disease control thereby increasing adherence. At the 12 month study visit all participants will be invited to participate in a 2 year extension to the study which will evaluate long term compliance with medication along with clinical outcomes. Additional participants will be invited to take part in

this long term monitoring arm of the study and will be randomised 1:1 to active monitoring or routine care. All participants taking part in this extension study will have their medication optimised using the GoutSMART approach to ensure that their urate level is at target of 0.3mmol/l or less.

For participants in the active care arm of the study ongoing monitoring of self-reported urate will be performed until participants meet criteria for disease remission. For the purposes of this study we will define disease remission to have been achieved if all three of the following outcomes have been achieved:

[figure not shown]
- 1) Resolution of clinically evident tophi
- 2) Urate levels at or below 0.3mmol/l over preceding 12 months (with minimum of 3 separate readings obtained in different months).
- 3) Resolution of gout flares (self-reported) for 12 months

When remission has been achieved by these criteria then participants will be given the option to reduce their dose of allopurinol in line with current best practise guidelines which suggest that maintaining urate below 0.36 mmol/l is sufficient to maintain remission, and that long term urate levels should not be held below 0.18mmol/l.

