Participants that were assigned to usual care will have their care optimised using the GoutSMART approach until they have achieved a urate at or below the target of 0.3mmol/l, but in line with usual clinical practise will have no further titration of their medication or outpatient clinical review after this point. Outcomes will be reviewed at 12 months, 24 months, and 36 months as part of the extension study.

In addition, all patients in the active care arm will be invited to participate in a dietary modification substudy during the extension phase. Those in whom aspects of dietary discordance with current BSR guidelines have been identified utilising the Food Frequency Questionnaire, will be offered an individualised plan of dietary modifications to be implemented over a period of time lasting up to three months. Regular measurements of urate levels and diet feedback will monitor progress.

Figure 2: Study Design Extension Phase

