6.1.4 Follow-up visit week 52 (and for extension study week 104 and 156)

Participants will be invited to the RDU clinic for review of secondary outcomes, or alternatively if hospital attendance is not appropriate due to recommendations to self-isolate or maintain social distancing due to the coronavirus pandemic then this assessment will be made by telephone. The patient diaries generated by the GoutSMART application will be reviewed and any adverse advents recorded. All participants will be asked to record the number of doses of medication missed in the preceding 2 weeks. A physical examination will be performed to assess the size and number of tophi or submitted images will be reviewed. Finger prick and/or serum urate will be measured along with blood tests of renal and liver function tests and oxypurinol levels.

All participants completing the study at week 52 will be offered participation of the extension phase of the study. Written information will have been provided prior to their week 52 review about the extension. Consent will be gained from those choosing to participate in the extension phase. A treatment plan will be formulated for all participants. Participants of the intervention arm in remission will be offered to reduce the dose of their urate lowering medication and self-reassess every two weeks (update urate levels, entering disease activity

data) until remission maintenance is achieved. Feedback will be provided in the usual GoutSMART application manner. Participants of the control arm will continue as per routine care. Once remission maintenance is achieved monthly urate reading will be requested. The participant will be asked to enter additional urate readings and QoL information during flares.

For those opting into the dietary lifestyle intervention arm, a personal management plan with dietary adjustments where appropriate will be formulated based on the Food Frequency Questionnaire which each participant will fill in at baseline. Participants will be asked to perform weekly urate measurements, weight measurements and report on flares via the app. Feedback will be provided by the research team at least weekly for the first 4 weeks, then monthly for three months. Participants will be asked to fill in the Food Frequency Questionnaire at extension baseline, monthly for three months and at the end of study.

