8.2 PROPOSED ANALYSES

The primary outcomes of the study will be the proportion of participants achieving urate level $\leq 0.3\text{mmol/l}$ at 24 weeks in participants receiving supported self-management compared to those receiving usual care. Comparison of proportions will be performed using the Chi-square test of independence, or Fishers Exact test for where expected values in any cell of the contingency table are less than 5, with results displayed as frequency (percentages). The proportion of participants achieving serum urate level $\leq 0.3\text{mmol/l}$ at all subsequent assessments will be analysed in the same fashion. Patients with undetectable levels of oxypurinol will be deemed to be non-compliant and a similar analysis will compare the proportion of participants in each treatment allocation that are non-compliant. For these analyses an intention to treat analysis will be performed with participants that have dropped out of the study being included as failing to reach target, or non-compliant with medication respectively.

Continuous outcome measures include the size in mm of the largest tophus at baseline (index tophus) measured at 52 weeks, and the number of clinically evident tophi evaluated at 52 weeks. Further continuous outcomes include the number of days lost at work due to gout flare, number of scheduled and unscheduled medical appointments/ hospital admissions, self report of number of doses of medication omitted in 2 weeks prior to study visits at week 24 and 52. Two-tailed independent student t-tests will be applied for between group comparisons of normally distributed data. Results will be displayed as mean \pm standard deviation (SD). A Mann Whitney U test (MWU) will be applied when the variables are not normally distributed, with results given as median (interquartile range IQR). Although a nominal value of significance of $p<0.05$ for these exploratory measures will be adopted, given the number of secondary outcomes listed a Bonferroni correction will be applied and reported alongside each result.

Although health reported quality of life data will be gathered this is exploratory data that will not be analysed directly but be used to inform the design of a larger health economic study.

Statistical analysis will be performed using Minitab version 16 (Minitab Inc., Pennsylvania, US) or the Statistical Package for Social Services version 19 (SPSS IBM Corp, NY State, US).

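### At weeks 104 and 156, section 8.2 specifies a between-arm urate comparison only at ≤0.30 mmol/l, so a protocol-planned dose reduction that settles between 0.30 and 0.36, offered only in the active arm, counts as a failure

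*Combined protocol and SAP*

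**What the plan says.** **Who may reduce.** Section 3.2 defines remission by three conditions: tophi resolved, urate at or below 0.30 mmol/l over the preceding 12 months, and 12 months without flares. Active-arm participants who meet them may lower their dose because "maintaining urate below 0.36 mmol/l is sufficient to maintain remission"; the same paragraph says urate should not be held below 0.18 in the long term. Section 6.1.4 confirms that intervention-arm participants in remission "will be offered to reduce the dose of their urate lowering medication", re-testing every two weeks "until remission maintenance is achieved". Section 1.1 gives the same rationale: "keeping urate levels at or below 0.36mmol/l should prevent recurrence of disease".

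**Usual care.** Section 3.2 has these participants optimised to ≤0.30, after which they "will have no further titration of their medication or outpatient clinical review after this point". Section 6.1.4 keeps controls on routine care.

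**What is analysed.** Section 8.2 compares the proportion at ≤0.30 at week 24 and says the same proportion "at all subsequent assessments will be analysed in the same fashion". Dropouts count as failures. No other urate threshold appears in 8.2.

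**What is listed.** Section 2.2.2 lists both ≤0.30 and ≤0.36 at weeks 24, 52, 104 and 156. It also lists "Proportion of patients achieving a dose reduction of urate lowering therapy in the extension phase whilst maintaining target urate levels". The synopsis has "Proportion of patients achieving a dose reduction of urate lowering therapy in the extension phase" with no urate condition.

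**The concern.** From the point of remission the two arms have different permitted urate ranges. An active-arm participant who has been at ≤0.30 for a year may reduce and settle at, say, 0.34. That is a good outcome by section 3.2 and a failure by the comparison in 8.2. Usual care has no planned step that does this. The effect runs in one direction, against the arm whose participants did well enough to reduce, and a lower active-arm rate at ≤0.30 could be read as loss of urate control. That matters because section 13.2 says the immediate goal is to inform a fully powered trial.

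There is a second, smaller gap. The dose-reduction endpoint in 2.2.2 depends on a target with no number attached. Elsewhere the target is 0.30, but the reduction is justified by 0.36. The same data could be scored in more than one way.

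**Working it through.** **1. The plan's own extension figure.** Section 8.1 gives 81% power with 20 per arm and 94% with 30 per arm for adherence of 90% v 50%. A pooled-variance normal approximation at two-sided 5% gives 0.813 and 0.943, so the figures reproduce. They concern adherence, not urate, and are not in dispute. The arm sizes 20 and 30 are used below.

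**2. Cost per participant.** Remission requires 12 months at ≤0.30, so every planned reducer starts as a success. One who settles above 0.30 and at or below 0.36 becomes a failure at ≤0.30 and stays a success at ≤0.36:
- 30 per arm: 1/30 = 3.3 points off the active rate
- 20 per arm: 1/20 = 5 points off the active rate
- usual care: 0 by any planned route

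Reductions that stay at or below 0.30 change nothing.

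**3. When it can start.** Original participants enter above 0.36 (section 4.2) and remission needs 12 months at ≤0.30, so for them no planned reduction can come before week 52. Fewer can have reduced by week 104 than by week 156.

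**4. What a given share would do.** Let m be the share of the whole active arm at 0.30–0.36 after a planned reduction. The documents do not give m, nor any extension urate rates, so every rate here is an assumption. If 12 of 30 (40%) reduce and 25/50/75% of them settle above 0.30, then m = 0.40 × 0.25/0.50/0.75 = 10/20/30%.

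Method: active rate = assumed rate − m. All pairs of binomial outcomes are enumerated, using chi-square without continuity correction, or Fisher's exact test if any expected cell is below 5, at two-sided 0.05.

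| Assumed rates at m = 0 (active v usual) | Result | n per arm | m = 0 | 10% | 20% | 30% |
|---|---|---|---|---|---|---|
| 80% v 80% | active significantly worse | 30 | 2% | 14% | 39% | 69% |
| 80% v 80% | active significantly worse | 20 | 2% | 10% | 28% | 53% |
| 90% v 70% | active significantly better | 30 | 47% | 14% | 2% | <1% |
| 90% v 50% | active significantly better | 30 | 95% | 69% | 35% | 12% |
| 90% v 50% | active significantly better | 20 | 83% | 53% | 24% | 8% |

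The 90% v 50% rows borrow 8.1's adherence rates as a stand-in only.

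**5. With the Bonferroni correction.** Section 8.2 reports a Bonferroni-corrected result beside each secondary result. Taking the 11 bullets in 2.2.2 as the count (an assumption), alpha = 0.05/11 = 0.0045. With 30 per arm:
- 80% v 80%, active significantly worse: 0.1/2/11/35%
- 90% v 50%, active significantly better: 74/35/11/2%

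**6. A small share.** With one such participant in 30 (m = 3.3%) at 80% v 80%, the uncorrected chance that the active arm looks significantly worse is 4.5%, against 2.1% at m = 0.

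**7. In counts.** 27/30 v 15/30 gives p = 0.0007. Four planned reducers at 0.30–0.36 make it 23/30, p = 0.032. Five make it 22/30, p = 0.063.

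**8. Dose-reduction endpoint.** Suppose 12 of 30 reduce and 6 settle at 0.30–0.36. The result is 12/30 under the synopsis wording or a 0.36 limit, and 6/30 if target means 0.30.

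**The case against.** **The ≤0.36 threshold is already an endpoint.** This is correct. A planned reducer at 0.34 fails one listed endpoint and passes its companion, and dose reduction is listed separately. The general sentence in 8.2 on comparing proportions could be read as covering ≤0.36 too. But that sentence follows the primary outcome, and the sentence on later assessments names only ≤0.30. What is missing is an analysis statement, not a measurement.

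**Section 8.2 does not name weeks 104 and 156.** True. They come in through its reference to all later assessments, read with the timing in 2.2.2 and the synopsis. That is the natural reading, but it is a reading.

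**The size is assumed.** This stands in full. Remission is demanding, reduction is optional, and m may be close to zero at week 104. The 80% v 80% case also sits awkwardly with the extension's premise that adherence is better in the active arm. The correction in step 5 shrinks the probabilities considerably.

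**A stronger reading.** A reader might infer that only active-arm participants can reach 0.30–0.36 through a lower dose. The documents do not support that. Controls stay under routine care, and nothing says how a dose change by their own physician would be handled. Usual-care participants may also drift into that range. Only the reduction offered by the protocol is one-sided.

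**Conclusion.** The point holds in a limited form. Followed as written, 8.2 scores a permitted outcome as a failure on the only urate threshold for which it states an analysis, by a planned route open to one arm. The firm figure is 3.3 or 5 points per affected participant. The probabilities above only illustrate what follows for an assumed m; if m = 0 there is no effect.

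A reader might infer that the extension's urate result is biased by a known amount, or that its power is lost. Neither follows: the documents give no m and no extension urate rates, and the extension is powered on adherence, which is also measured by oxypurinol and missed doses. The week 24 primary and week 52 analyses are untouched.

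The missing level for the dose-reduction endpoint is a real ambiguity in the available text, though Figure 2 is not shown and may settle it.

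Severity is minor to moderate: an exploratory secondary comparison in the extension of a feasibility study.

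**What to change.** 1. **Section 8.2.** State that the proportion at ≤0.36 mmol/l is compared between arms at weeks 104 and 156, with the same test and the same dropout-as-failure rule, and reported together with ≤0.30. Add that a lower active-arm rate at ≤0.30 is not to be read as loss of control without the ≤0.36 result and a descriptive count of active-arm participants at 0.30–0.36 after a planned post-remission reduction. Leave weeks 24 and 52 as they are.
2. **Section 2.2.2 and synopsis.** Define the dose-reduction endpoint as a urate-lowering dose below the dose at remission, with visit urate ≤0.36 mmol/l, at week 104 and at week 156. Give the number who reached remission alongside. This is not needed if Figure 2 already sets a level.

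**Downside.** At ≤0.36, participants in either arm who are not in remission count as controlled at 0.30–0.36, including usual-care participants who have drifted up after being optimised to ≤0.30. That could hide the loss of control the extension should detect, so ≤0.36 should not replace ≤0.30; the two must be shown side by side.

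**Cost.** Protocol and analysis wording, plus recording the dose at remission on the case report form. Urate is already measured at both visits and ≤0.36 is already listed, so no new visits, tests or participants are needed.

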3.3 COVID -19

Any research activity continues to be effected by the current COVID-19 pandemic. Any research activity will be carried out in compliance with prevailing Scottish and UK Government instructions and guidance as well as the local R&D regulations. This includes continuous risk assessments to minimize the exposure to COVID-19 to any participant, in particular those who are required to socially distance, self-isolate or shield. In practice this will require adaptations in most activities. All scheduled review will be carried out via telephone rather than face to face unless clinically indicated. Consent may not be taken in person but the information is provided prior to a review, discussed via telephone and the participant asked to sign consent in their home forwarding the documents via email or post.

4 STUDY POPULATION

4.1 NUMBER OF PARTICIPANTS

We aim to recruit approximately 60 participants. Recruitment will remain open until sufficient numbers of recruited participants has been reached. Additional participants satisfying the same inclusion and exclusion criteria (but without any urate threshold requirement) will be recruited into the extension study to ensure sufficient power is maintained). An equal number of control participants will be recruited for the purposes of the gut microbiota analysis.

4.2 INCLUSION CRITERIA

Subjects must meet all of the following inclusion criteria to enter the study:

- Evidence of a personally signed and dated informed consent document indicating that the subject has been informed of all aspects of the study.
- Adult male or female aged ≥ 18 years.
- Confirmed clinical diagnosis of gout as per ACR/EULAR criteria (Neogi T, 2015).
- Physician recommendation that initiation or escalation of urate lowering therapy (Allopurinol or Febuxostat) is required guided by further monitoring of serum urate levels.
- No previous adverse reaction to Allopurinol or Febuxostat.
- Serum urate >0.36 mm/L.
- Patient has a smart phone and is able to use application.

For the gut microbiota part of this study control participants must be:

- Adult male or female aged ≥ 18 years.
- Evidence of a personally signed and dated informed consent document indicating that the subject (or a legally acceptable representative) has been informed of all aspects of the study.

For the extension study

- Patient has completed week 52 of original study
- Evidence of a personally signed and dated informed consent document indicating that the subject has been informed of all aspects of the extension study.

